8.5 Treatment Compliance

IMP will be provided by the sponsor and delivered to participating sites by the Central Drug Repository selected for the study. All subjects will be infused under the supervision of the PI and will receive the IMP dose ordered by the PI, and these data will be recorded in the eCRF. Only subjects who have been enrolled into the study will receive IMP. For more information on IMP dispensing and accountability, please see Section 13.

During the Waiting Period for IMP treatment, commercial product will be infused under the supervision of the PI according to standard care, and the data will be recorded in the eCRF. If a subject is enrolled directly from a clinical trial, the PI will make the determination which commercial product the subject will receive, in consultation their treating physician.

8.6 Protocol Deviations

Every effort will be made to avoid deviations from the protocol during the conduct of the study. When protocol deviations do occur, the Investigator should promptly inform the Monitor, and the implications of each deviation must be reviewed and discussed. Any deviation must be documented, stating the reasons, date, actions taken, and the impact for

the subject and/or study for each deviation. This documentation must be kept in the Sponsor Files, Investigator Files, and recorded in the eCRF. In case of any major protocol deviations (i.e., violations), the PI and sponsor will decide on the further participation of the affected submitted to the IRB/IEC according to the requirements of each of these institutions.

Unique scheduling windows are indicated throughout the protocol with the use the “±” or “+” symbols. Protocol-related activities that occur outside the scheduled time point but within the allotted “±” or “+” windows are allowed and are not considered deviations.

8.7 Data Safety Monitoring Board (DSMB)

In addition to the Sponsor and PI’s responsibility for oversight, study oversight will be under the direction of an independent DSMB. The DSMB will be responsible for ongoing review of safety data. The PI will assess seriousness, causality, and intensity (severity) of an adverse event.

The processes, composition, and intervals of meetings will be described in detail in a separate DSMB charter written in accordance with the FDA *Guidance* [March, 2006].

The DSMB will include members with expertise in immunology and experience in clinical trials with immunoglobulin product. The DSMB will at minimum meet after all subjects in Group 1 have received their first infusion of IMP and the immunogenicity results are available, prior to Infusion 2. They will meet again once a further 10 subjects have received their first infusion of IMP and immunogenicity results are available prior to Infusion 2. These subjects will continue on IMP during review of safety data, but no further subjects will receive IMP until DSMB and FDA provide safety evaluation. At any time a thrombotic or hemolytic event is suspected or reported the DSMB will review the data of individual subjects and if needed additional subjects to make a determination.

All immunogenicity data except for the screening data, baseline and Infusion 2 (prior to infusion) will be batch tested. The DSMB can request that the retention samples for immunogenicity testing (anti-β2GPI and β2GPI-DI antibodies) or Protein C and S can be tested at any time. Once Group 1 and Group 2 have been approved, a DSMB meeting will take place after 20 subjects in Group 3 receive at least 6 doses of IMP. In the event any safety concerns are raised in the periods between meetings by SAEs, the DSMB Chair will hold ad hoc meetings to ensure the safety of all subjects and determine whether the concern warrants applying the stopping rules.

The DSMB will provide its analysis and conclusions to ProMetic BioTherapeutics, to the IRBs, and to the FDA. The DSMB Charter is a separate document detailing the composition, governance, meeting preparation and conduct, voting rules and stopping rules.

9 Concomitant and Prohibited Medications

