6.10 Immunogenicity Testing

Immunogenicity testing for the detection of antibodies to $\beta 2$ GPI and $\beta 2$ GPI -DI will include the following tests:

- $\beta 2$ GPI Domain 1 QUANTA Flash Kit, INOVA Diagnostics
- $\beta 2$ GPI IgG Ab QUANTA Flash Kit, INOVA Diagnostics
- $\beta 2$ GPI IgM Ab QUANTA Flash Kit, INOVA Diagnostics

Blood samples for detection of antibodies to $\beta 2$ GPI and $\beta 2$ GPI -DI will be drawn at the following time points:

- **All subjects** at Screening
- **All subjects** before administration of IMP or CP at infusions 1 (baseline value), 2, 4, and 8, LTSV before infusion of the subject's standard immunoglobulin treatment

- Retention samples will be drawn at every visit for subjects on **IMP treatment**, from baseline through the LTSV

If any subject after receiving IMP seroconverts from negative to positive, with an elevated antibody titer at least 12 weeks apart, as defined in Section 8.1.1, then all prior retention samples for β 2GPI and/or β 2GPI-DI for all subjects should be analyzed.

6.11 3-4 Hour Post-infusion Safety Testing – Indicators of Thrombosis

For **all subjects**, blood samples will be drawn 3-4 hours after the end of IMP/CP infusion at Infusion 1, 2, 4, 8, 12 and 16.

Tests include:

- D-dimers
- Retention sample for protein C and protein S determination, in case d-dimer results indicate potential thrombosis or the PI determines a need for such testing from his evaluation (Note: a retention sample for protein C and protein S will also be taken at Screening to allow for a comparison of the subject's baseline status in the event of a later thrombotic episode or thromboembolic vascular event.)

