8.1.1 Immunogenic Reactions

Diagnosis of an immunogenic reaction that may lead to a thrombotic event will be based on treatment-emergent positive anti- β 2GPI and β 2GPI-DI antibody titers, defined as an antibody titer of ≥ 40 U found twice on tests that are at least 12 weeks apart and/or on treatment-emergent positive anti- β 2GPI and β 2GPI-DI antibody titers > 20 U but < 40 U in combination with a treatment-emergent thrombotic or thromboembolic event (Unlu et al., 2015) by these definitions will be considered significant events. If any subject after receiving IMP seroconverts from negative to positive, with an elevated rising antibody titer at least 12 weeks apart, then all prior retention samples for β 2GPI and/or β 2GPI-DI for all subjects should be analyzed.

Subjects who develop treatment-emergent anti- β 2GPI and/or β 2GPI-DI antibody titers > 20 U following exposure to IMP will be followed closely by the investigator for thrombotic and/or thromboembolic events. These subjects will have periodic (no more than 8 weeks apart) anti- β 2GPI and β 2GPI-DI antibody titer testing until they have completed 52 weeks of treatment with IMP or until immunogenicity titers have stabilized or are declining over 3 consecutive treatment cycles (21 or 28 day cycles), whichever is later.

As shown in Figure 2:

1. Any subject who has a significant event as defined above for anti- β 2GPI and/or β 2GPI-DI antibodies while being treated with IMP will permanently discontinue treatment with the IMP. The subject will remain in the study for safety assessments up to the time of the final follow-up phone call after LTSF (see Section 7.11).
2. The occurrence of two such significant events as defined above for anti- β 2GPI and/or β 2GPI-DI antibodies will be referred to the DSMB for an urgent ad-hoc review to determine if this qualifies as a potential study-stopping event as defined above.

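### Antibody titers after Infusion 2 are batch tested with no stated turnaround, so in a symptom-free subject the antibody safety rules may not be triggered in time

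*Protocol*

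**What the plan says.** Protocol Section 6.10 schedules titers of antibodies to β2GPI and β2GPI-DI at Screening and then "before administration of IMP or CP at infusions 1 (baseline value), 2, 4, and 8, LTSV before infusion" of the subject's standard product. It adds: "Retention samples will be drawn at every visit for subjects on" IMP. These retention samples are stored and are not tested routinely.

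Section 8.7 sets when the assays are run: "All immunogenicity data except for the screening data, baseline and Infusion 2 (prior to infusion) will be batch tested". Neither the protocol nor the SAP says how often a batch is run or how soon its results are reported.

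Section 8.1.1 ties actions to the titers:

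- Two-titer criterion: a titer of 40 U or more "found twice on tests that are at least 12 weeks apart" is a significant event.
- Event-linked criterion: a titer above 20 U but below 40 U "in combination with a treatment-emergent thrombotic or thromboembolic event" is also a significant event.
- A subject with either kind of event on IMP "will permanently discontinue treatment with the IMP".
- A subject with any treatment-emergent titer above 20 U is watched closely for thrombosis and retested at intervals of 8 weeks or less.
- Two or more confirmed subjects put IMP on hold for everyone (also Section 8.1).

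No section explains how these rules work while results are waiting for a batch.

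**The concern.** The two-titer criterion is a warning signal, meant to act before any clot occurs. It can do so only if the results are known while the subject is still being dosed. Until a batch is run, the investigator has no reason to start the 8-weekly retest or stop IMP, and the DSMB has no basis for a hold. Section 6.2 asks staff to review earlier laboratory results before each infusion, but a sample that has not been run has no result to review.

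The approvals for Groups 1 and 2 (Section 1.4) do not settle this. The reviews behind them were planned around the sample taken before Infusion 2 (Section 3.1), so they do not cover later rises. The rules apply to every subject throughout IMP treatment, including the children in Group 3.

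**Working it through.** The plan gives no figure to reproduce here. The check is of the calendar.

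**Inputs.** Titers are scheduled before Infusions 2, 4 and 8 and at the LTSV (Section 6.10). There are 17 infusions on the 21-day cycle and 13 on the 28-day cycle, and the LTSV is at Week 51 or 52 (Table 4). Week of an infusion = (infusion number − 1) × 3 or × 4, which matches Table 4.

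| Post-dose titer | 21-day cycle | 28-day cycle | Exempt from batching? |
|---|---|---|---|
| Infusion 2 | Week 3 | Week 4 | Yes |
| Infusion 4 | Week 9 | Week 12 | No |
| Infusion 8 | Week 21 | Week 28 | No |
| LTSV | Week 51 | Week 52 | No |

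**Pairs at least 12 weeks apart.**

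- Infusions 2 and 8: 21 − 3 = 18 or 28 − 4 = 24 weeks.
- Infusions 4 and 8: 21 − 9 = 12 or 28 − 12 = 16 weeks.
- Infusion 2 and LTSV: 48 weeks on both cycles.
- Infusion 4 and LTSV: 42 or 40 weeks.
- Infusion 8 and LTSV: 30 or 24 weeks.

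That makes five qualifying pairs per cycle, and none has both results exempt from batching. Only the two pairs ending at Infusion 8 are complete before the last IMP dose at Week 48.

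**Infusions still to come.** After the Infusion 8 visit, 17 − 8 = 9 or 13 − 8 = 5 infusions remain.

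**First rise at Infusion 4.** If the result were known, a retest would be due by Week 9 + 8 = 17 or Week 12 + 8 = 20. If it is not known, the next scheduled titer is at Week 21 or 28, and that sample is batched too.

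**First rise at Infusion 8.** The only scheduled confirmation is the LTSV, after the last IMP dose. If the Infusion 8 result were known, the 8-weekly retest would start. The 12-week criterion could then be met from Week 21 + 12 = 33 or Week 28 + 12 = 40. With retests at the full 8-week spacing it could be met at Week 37 or 44. All of these fall before Week 48.

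**Sensitivity to the unstated delay.** The delays below are assumptions. The counts are infusions given after the Infusion 8 visit and before its result is known.

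| Assumed delay (weeks) | 21-day cycle | 28-day cycle |
|---|---|---|
| 4 | 1 | 0 |
| 8 | 2 | 1 |
| 12 | 3 | 2 |
| 26 | 8 | 5 |
| 52 | 9 | 5 |

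**The case against.** A reader might infer that the antibody rules cannot be triggered at all. The documents do not support that, for these reasons:

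- Batch testing does not mean one batch at the end of the study. Frequent batches could satisfy every rule.
- The event-linked criterion does not depend on routine batches. A suspected thromboembolic event leads to testing of that subject's retention samples (Sections 6.12.2.2 and 6.12.3.3), and the calls after each infusion also consider whether such testing is needed (Sections 7.5 and 7.6). A confirmed thromboembolic event stops IMP for that subject without any titer (Section 8.1.2).
- A titer above 20 U before Infusion 2 is seen outside the batches and can start the follow-up.
- The DSMB may ask for retention samples to be tested at any time and has a planned Group 3 review. Section 8.7 sets it after 20 subjects have had at least 6 doses; SAP Section 6.2 sets an interim analysis after 20 have completed 6 months.
- The DSMB charter is a separate document and may state timing.

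All of this stands, but none of it closes the gap for a symptom-free subject with a later rise. Event-driven testing waits for the suspected event. At exactly 6 doses (Week 15 or 20), the scheduled post-dose titers are from Infusions 2 and 4, only 6 or 8 weeks apart, so they cannot meet the 12-week criterion. Six months (about Week 26) is past Infusion 8 on the 21-day cycle but not on the 28-day cycle, and the SAP does not say that batched titers feed that review.

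A reader might also set the 30- or 24-week gap between Infusion 8 and the LTSV against the 8-week limit and call it a breach. It is not one. The gap comes from the routine sampling schedule and would exist with every sample run on receipt, while the 8-week rule applies only after a titer above 20 U.

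**Conclusion.** The concern holds in a limited form. A stated batching rule and stated safety rules conflict, and the documents do not reconcile them. For a symptom-free subject whose titer first rises at Infusion 4 or later, three things may come late: the 8-weekly retest, discontinuation under the two-titer criterion, and the two-subject hold built on that criterion. On the scheduled samples, the two-titer criterion always needs at least one batched or specially requested result.

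The size depends on a delay that neither document gives. For an Infusion 8 result it runs from 1 infusion (21-day) or none (28-day) at an assumed 4-week delay, up to 9 or 5 if results come only after treatment ends. Counting 10 or 6 would overstate it, because Infusion 8 is given at the visit where the sample is drawn. Part of the wait also belongs to the confirmation rule itself: even with scheduled samples run on receipt, the two-titer criterion cannot be met before Week 21 or 28.

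The conclusion assumes that Section 8.7 means what it says and that no other document sets a turnaround. A charter that does so could resolve it.

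**What to change.** Reconcile Sections 8.7, 8.1.1 and 6.10 in one of two ways:

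- Take the Infusion 4 titer, the Infusion 8 titer and the 8-weekly follow-up titers out of the batch-tested set.
- Or state a maximum batch turnaround short enough for the Section 8.1.1 rules to operate as written.

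The follow-up titers must be included. As worded, Section 8.7 batches them as well, so releasing only Infusions 4 and 8 would leave the retest rule without timely results. If the DSMB charter already sets a turnaround, the protocol should state it or refer to it.

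Titer thresholds, confirmation intervals and clinical actions are not at issue and stay unchanged. The assays and samples are the same, so the cost is a small amount of laboratory logistics.

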9.1 Commercial Product

Subjects who prior to entering the study were receiving commercially available IGIV will continue to receive the same product. Subjects who prior to entry were receiving IGSC or who were receiving another investigational IGIV will receive the commercially available IGIV chosen by the Investigator in consultation with their treating physician.

9.2 Concomitant Medications

The administration of concomitant medications, including topical steroids for skin conditions, steroid eye drops, chronic use of inhaled steroids for asthma, and intranasal steroids for rhinitis, is permitted during the study period in keeping with the standard of care for subjects with PIDD. A brief course of systemic steroids (i.e., a steroid burst) is allowed for treatment of a short-term condition such as an asthma exacerbation or poison ivy exposure. Any medications, including non-prescription medications, taken by the subject from 21 days (± 2 days) or 28 days (± 2 days) (depending on subjects' dosing interval) before baseline (Infusion 1) through the end of the study and the reason for use will be recorded and captured in the eCRF.

Hydration practices are allowed during the study. All fluids administered and the volumes used will be recorded and captured in the eCRF.

The use of pre-medication for pain relief and/or diphenhydramine prior to an IMP infusion is only permitted if the subject is using these pre-medications as part of routine IGIV or IGSC treatment.

9.3 Prohibited Medications

The following medications are prohibited in this study:

- Other immune globulin therapy after Baseline IMP infusion 1.
- Immunosuppressive drugs, e.g., chemotherapy drugs.
- Oral or parenteral corticosteroid at a dose ≥ 0.15 mg/kg/day prednisone or equivalent, except a steroid burst as described in Section 9.2.
- Continuous antibiotics intended for prophylaxis of bacterial infections.

9.4 Other Restrictions

Medications from other research studies or clinical studies are not permitted.

10 Reporting of Adverse Events

10.1 Definitions

10.1.1 Adverse Event

An AE is any untoward medical occurrence (whether or not considered to have a causal relationship to IMP) in a study subject administered an IMP. Therefore, an AE can be any unfavorable and unintended sign (including a clinically significant laboratory finding), symptom, or disease temporally associated with the use of an IMP, whether or not related to the IMP. For the purposes of this protocol, all AEs occurring during the study are considered treatment-emergent AEs (TEAEs) associated with the use of the immunoglobulin product (either IMP or CP), whether or not the AE is determined to be product related.

10.1.2 Adverse Drug Reaction (ADR)

According to the FDA *Guidance for Industry Adverse Reactions Section of Labeling for Human Prescription Drug and Biological Products — Content and Format (January 2006)*, an *adverse reaction* is an undesirable effect, reasonably associated with the use of a drug, that may occur as part of the pharmacological action of the drug or may be unpredictable in its occurrence. This definition does not include all adverse events observed during use of a drug, only those for which there is some basis to believe there is a causal relationship between the drug and the occurrence of the adverse event. Adverse reactions may include signs and symptoms, changes in laboratory parameters, and changes in other measures of critical body function, such as vital signs and ECG.

10.1.3 Infusional and Temporally Associated Adverse Events

AEs that occur during the infusion of the IMP or CP will be recorded as Infusional AEs. Temporally associated AEs are those that occur during the infusion or within 72 hours following the end of the infusion, regardless of other factors that may impact a possible causal association with IMP/CP administration.

10.1.4 Serious Adverse Events (SAEs)

All AEs must be evaluated as potential serious adverse events (SAEs). An SAE is any untoward medical occurrence that at any dose:

- Results in death.
- Is life-threatening (i.e., the subject was at immediate risk of death from the AE as it occurred. (This does not include an event that, had it occurred in a more severe form or was allowed to continue, might have caused death).
- Requires inpatient hospitalization or prolongation of existing hospitalization.
- Results in persistent or significant disability/incapacity.

- Is a congenital anomaly/birth defect (in the child of a subject who was exposed to the study drug) or
- Is a medically important event or reaction:
 - Events that did not result in death or hospitalization but may, based on appropriate medical judgment, jeopardize the subject or require intervention, to prevent one of the outcomes in the definition of SAE listed above, should also be considered SAEs.

10.1.5 Adverse Event Severity

The Investigator will assess the severity of AEs according to the criteria below:

- **Mild:** The AE is transient and does not interfere significantly with the subject's normal functioning level. The AE resolves spontaneously or may require minimal therapeutic intervention.
- **Moderate:** The AE produces limited functional impairment and may require therapeutic intervention. The AE produces no sequelae.
- **Severe:** The AE results in significant impairment of function and may lead to temporary inability to resume the subject's normal life pattern. The AE produces sequelae which require prolonged therapeutic intervention.

10.1.6 Adverse Event Relationship to IMP or CP

The following 4-point scale will be used by the Investigator to rate the relationship of the adverse event to the study product, and final determination of causality will be established by the Sponsor:

- **Definitely related:** A clinical event (including laboratory test abnormality) occurring in a plausible time relationship to drug administration, and which cannot be explained by concurrent disease or other drugs or chemicals. The response to withdrawal of the drug (de-challenge) should be clinically plausible. The event must be definitively associated pharmacologically, using a satisfactory re-challenge procedure, if necessary.
- **Probably related:** A clinical event (including laboratory test abnormality) with a reasonable time sequence to administration of the drug, unlikely to be attributed to concurrent disease or other drugs or chemicals, and which follows a clinically reasonable response on withdrawal (de-challenge). Re-challenge information is not required to fulfill this definition.
- **Possibly related:** A clinical event (including laboratory test abnormality) with a reasonable time sequence to administration of the drug, but which could also be

explained by concurrent disease or other drugs or chemicals. Information on drug withdrawal may be lacking or unclear.

- **Not related:** An event for which sufficient information exists to conclude that the etiology of the event is unrelated to the IMP.

Causality will be assessed as follows:

The Investigators will assign causality at their respective sites during the study, with final determination of causality established by the Sponsor. The DSMB will review the assigned causality for all AEs and SAEs prior to database lock. This assignment will be included in the study database and final study report. As noted in the FDA *Guidance for Industry Adverse Reactions Section of Labeling for Human Prescription Drug and Biological Products — Content and Format*, decisions on whether there is some basis to believe there is a causal relationship will be based on factors such as: (1) the frequency of reporting, (2) whether the adverse event rate for the drug exceeds the placebo rate, (3) the extent of dose-response, (4) the extent to which the adverse event is consistent with the pharmacology of the drug, (5) the timing of the event relative to the time of drug exposure, (6) existence of challenge and de-challenge experience, and (7) whether the adverse event is known to be caused by related drugs.

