2.3.4 Safety Objectives

The safety objectives are:

- To examine the safety and tolerability of the IMP
- To collect adverse events (AEs) from the start of the signing of informed consent to 21 days (± 2 days) or 28 days (± 2 days) after the last infusion, depending on the subject's treatment schedule
- To examine total AEs and the observed proportion of AEs considered by the Sponsor to be IMP related;
- To examine AEs temporally associated (during and within 72 hours after the end of the infusion) with the IMP infusion, which will be recorded regardless of relationship to the IMP
- To examine infusion and rate-related AEs, regardless of relationship to the IMP

- To monitor safety approximately 7 days post infusion
- To examine long-term safety with virology testing from Screening to the Long-Term Safety Visit (LTSV)
- To monitor for immunogenic reactions by testing for antibodies to β 2GPI and β 2GPI-DI, from baseline to the LTSV
- To monitor for thrombogenicity and hemolysis by performing post-infusion clinical evaluations and laboratory testing

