10.3 Eliciting and Reporting of Other Adverse Events

AEs will be captured from signing of Informed Consent/Assent to until 21±4 days or 28±4 days following the last infusion. AEs and ADRs will be elicited and reported as follows:

The condition of the subject will be monitored throughout the study. At each visit, AEs will be elicited using a standard non-leading question such as "*How have you been since the last visit / during the previous study period?*" AEs will also be elicited through the use of Subject Diary cards, which the Investigator will review in detail with the subject at each visit, ensuring accuracy and completeness of entries recorded by the subject.

The staff will also ask specific questions during phone calls to determine whether a work-up for hemolysis and/or thrombosis is necessary. During the phone calls, the staff will ask open-ended questions about the subject's wellbeing and to ensure that AEs are being documented in the Subject Diary. The study staff will review these specific questions with the subject and ensure subject is completing the diary. (Section 6.12.3)

Any AE or ADR occurring during the study will be noted in detail on the appropriate pages of the eCRF. If the subject reports several signs or symptoms, which represent a single syndrome or diagnosis, the latter should be recorded in the eCRF. The Investigator will grade the severity of all AEs or ADRs (mild, moderate, or severe), the seriousness (non-serious or serious) and relatedness, with final determination of causality established by the Sponsor, as defined in Section 10.1.

In the event of abnormal laboratory findings considered clinically significant by the Investigator, the tests will be repeated and followed-up, as needed. Diseases, signs and symptoms, and/or laboratory abnormalities already existing before the first administration of IMP are not considered as AEs when observed at a later stage unless they represent a worsening.

The Investigator should always provide detailed information concerning any abnormalities and the nature of, and reasons for any necessary action(s), as well as any other observations or comments, which are useful for the interpretation and understanding of the subjects' AEs or ADRs.

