- The number and proportion of infusions with which one or more TAAEs and infusional TEAEs are associated;
- The number of temporally associated TAAEs and infusional TEAEs per infusion;
- Number of infusions/subject where infusion rate was decreased due to an AE, and
- Subjects with at least one infusion where rate was decreased due to an AE

The operational definition of adverse reaction/suspected adverse reaction for analysis purposes will be all AEs meeting any of the following criteria:

- (a) The event began during or within 72 hours following the last IMP infusion;
- (b) The event was considered by the investigator and/or the sponsor to be at least possibly related to the IMP administration; or
- (c) The causality assessment was missing or indeterminate.

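### The safety objective counts only AEs the Sponsor considers related, and the SAP's relationship tables name no assessor, although the adverse-reaction definition accepts either rating

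*Protocol*

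**What the plan says.** Protocol 10.1.6 sets a four-point scale for the investigator and adds that "final determination of causality will be established by the Sponsor". It repeats this under the causality procedure ("The Investigators will assign causality at their respective sites during the study, with final determination of causality established by the Sponsor"), and Protocol 10.3 says the same of the eCRF grading ("relatedness, with final determination of causality established by the Sponsor, as defined in Section 10.1"). Protocol 10.1.6 continues: "The DSMB will review the assigned causality for all AEs and SAEs prior to database lock", and then "This assignment will be included in the study database and final study report". It does not say which rating that assignment is, or whether both are kept.

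The safety objective in Protocol 2.3.4, repeated in the synopsis and in SAP 2.3, concerns "the observed proportion of AEs considered by the Sponsor to be IMP related".

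Two places take a different view. Protocol 8.7 says the PI assesses causality and does not mention the Sponsor. The operational definition of an adverse reaction (synopsis, Protocol 12.3.4, SAP 11.1) includes the criterion "The event was considered by the investigator and/or the sponsor to be at least possibly related to the IMP administration", so one positive rating is enough.

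Three SAP summaries depend on relatedness without naming the assessor: the rate of at least possibly related TAAEs (11.1), TEAEs by relationship (11.2) and related TEAEs leading to discontinuation (11.4).

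**The concern.** Nobody is blinded and there is no concurrent control, so relatedness is a judgement made with full knowledge of the product. The party with an interest in the result has the last word, and the stated objective is built on that party's view alone. No passage limits the Sponsor to raising a rating, asks for a reason when a rating changes, or says how disagreements are reported.

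At stake is the related-AE proportion, together with the relationship tables if they are built on the final value. Section 10.1.6 covers commercial product as well as IMP, and the SAP shows safety for the two periods side by side. The Sponsor's determination would therefore enter both columns.

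**Working it through.** The plan has no figure to reproduce here, because the point concerns a counting rule. The check puts the documents' rules side by side.

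**Inputs**
- Sponsor-only rule: the objective in Protocol 2.3.4 and SAP 2.3, with finality from Protocol 10.1.6 and 10.3.
- Either-assessor rule: criterion (b) of the adverse-reaction definition in Protocol 12.3.4 and SAP 11.1.
- Full adverse-reaction definition: criterion (b), or onset during or within 72 hours of the infusion (a), or missing or indeterminate causality (c). The table takes both ratings as present, so (c) does not arise.

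**Does the event count? (1 = yes, 0 = no)**

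| Investigator: related | Sponsor: related | Sponsor-only | Either assessor | Adverse reaction, onset after 72 h | Adverse reaction, onset within 72 h |
|---|---|---|---|---|---|
| No | No | 0 | 0 | 0 | 1 |
| No | Yes | 1 | 1 | 1 | 1 |
| Yes | No | **0** | **1** | 1 | 1 |
| Yes | Yes | 1 | 1 | 1 | 1 |

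The Sponsor-only and either-assessor rules differ in one row: investigator yes, Sponsor no.

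**Size.** Let N be all AEs, a those both rate related, b those only the investigator rates related, and c those only the Sponsor rates related.
- Sponsor-only proportion: (a + c)/N.
- Either-assessor proportion: (a + b + c)/N.
- Difference: (a + b + c)/N − (a + c)/N = b/N.

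Each downgrade thus removes exactly one event from the numerator. The documents give no value or expected range for b, so no number can be put on b/N. Against an investigator-only proportion, (a + b)/N, the Sponsor-only figure could be higher or lower, since the difference is (c − b)/N. Against the either-assessor rule it can only be equal or lower.

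**Where the rule matters**
- Objective in Protocol 2.3.4 and SAP 2.3: Sponsor-only by its own wording, so b is lost.
- SAP 11.1 related TAAE rate, 11.2 and 11.4: assessor not named. If the final value is used, b is lost; if either rating counts, it is not.
- Adverse-reaction analysis: the investigator-yes, Sponsor-no row counts 1 at any onset time, provided the investigator's rating is still available. If only the Sponsor's were available, an event starting within 72 hours would still count under (a), but a later one would not count under (b).
- Protocol 12.3.4 test that fewer than 40 per 100 infusions have a temporally associated AE: it takes all AEs whatever their cause, so b has no effect.

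**The case against.** The strongest reply is that the documents already protect what matters most. The protocol's only tested safety endpoint ignores causality. The adverse-reaction analysis uses the either-assessor rule and also counts events by timing and by missing causality. The stopping criteria in Protocol 8.1 rest on antibody titres and confirmed thromboembolic or hemolytic events, not on the causality scale. An independent DSMB reviews causality before lock, and Protocol 14.2 has data changes tracked electronically. The Sponsor may also raise ratings, and the objective states openly whose view it uses. On this argument, naming the assessor would be enough.

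Most of that stands and limits the point. It does not remove it: the objective still loses every downgraded event by its own definition, and the DSMB is given no stated power to change a rating.

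A reader might go further and infer three things the documents do not support:
- **That only the Sponsor's rating is stored.** The sentence on what enters the database does not say whose assignment it means. The either-assessor definition implies that both ratings exist, and Protocol 10.3 has the investigator grade relatedness for the eCRF. The gap is that retention of both is never stated.
- **That a downgrade lowers the adverse-reaction results.** It does not if both ratings are kept.
- **That expedited reporting under Protocol 10.4.3 is weakened.** That section does not say an investigator's related rating is disregarded, and Protocol 10.4.1 sends every SAE to the Safety Department within 24 hours whatever its cause.

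**Conclusion.** The point holds in limited form. The plan applies the Sponsor's view to the related-AE objective and either assessor's view to adverse reactions, names the PI alone in Protocol 8.7, and names nobody in three SAP summaries. For the objective, the downward route follows from the rule itself. For the SAP 11.1, 11.2 and 11.4 summaries it is a possibility left open by silence, not a stated rule.

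The effect is b/N, the share of AEs that only the investigator rates related. This assumes some disagreements occur; with none, the rules give the same answer. The primary SBI endpoint and the protocol's 40-per-100 test are unaffected. The change is worth making because it is cheap and closes a bias route in an unblinded safety report, not because a main conclusion depends on it.

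**What to change.** - In Protocol 10.1.6, state that the investigator's and the Sponsor's ratings are both kept, as separate fields, and align Protocol 8.7 and 10.3 with that.
- In Protocol 2.3.4 (and the synopsis), SAP 2.3, and SAP 11.1, 11.2 and 11.4, count an AE as related if either assessor rates it at least possibly related. This matches the existing adverse-reaction definition, so the relatedness tables and the adverse-reaction table share one rule.
- Add a listing of all events on which the two ratings differ, showing both.

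The cost is one database field, if it does not already exist, and wording changes in both documents, including a restated objective. The downside is a related-AE rate that may be higher than under the Sponsor's view alone.
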